5.7.5. Immunogenicity

Frequencies and percentages will be tabulated for the following:

- participants with pre-existing ADA, and
- participants who are treatment-emergent ADA positive (TE-ADA+) to LY3454738.

Treatment-emergent ADAs are defined as those with a titer 2-fold (1 dilution) greater than the minimum required dilution if no ADAs were detected at baseline (treatment-induced ADA) or those with a 4-fold (2 dilutions) increase in titer compared with baseline if ADAs were detected at baseline (treatment-boosted ADA). For the TE ADA+ participants, the distribution of maximum titers will be described. The frequency of neutralizing antibodies, when available, will also be tabulated for the TE-ADA+ participants.

The relationship between the presence of antibodies and the PK parameters and PD response including safety and efficacy to LY3454738 may be assessed.

5.7.6. Special Safety Topics, including Adverse Events of Special Interest

In addition to general safety parameters, safety information on specific topics of special interest will also be presented. Additional special safety topics may be added as warranted. The topics outlined in this section include the protocol-specified AESI.

In general, for topics regarding safety in special groups and circumstances, patient profiles and/or patient listings, where applicable, will be provided when needed to allow medical review of the time course of cases/events, related parameters, patient demographics, study drug treatment and meaningful concomitant medication use. In addition to the safety topics for which provision or review of patient data is specified, these will be provided when summary data are insufficient to permit adequate understanding of the safety topic.

5.7.6.1. Abnormal Hepatic Tests

Analyses for abnormal hepatic tests will involve 4 laboratory analytes: ALT, AST, total bilirubin, and ALP. In addition to the analyses described in Section 5.7.3, this section describes specific analyses for this topic.

The central laboratory reference ranges (CLRM reference ranges) will be used for these laboratory assessments (ALT, AST, total bilirubin, and ALP).

Analyses for change from baseline to last observation, change from the baseline value to the minimum value during Period 2 and 3, change from the baseline value to the maximum value during Period 2 and 3, and treatment-emergent high or low laboratory results at any time are described in Section 5.7.3.

The patients with the following abnormal elevations in hepatic laboratory tests at any time will be listed for both Period 2 and 3:

- ALT measurement \geq 3 times, \geq 5 times and \geq 10 times the central laboratory ULN.
- AST measurement ≥ 3 times, ≥ 5 times and ≥ 10 times the central laboratory ULN.
- Total bilirubin measurement ≥ 2 times the central laboratory ULN.
- ALP measurement \geq 1.5 times the central laboratory ULN.

5.7.6.2. Renal Function Effects

Effects on renal function will be assessed through analysis of elevated creatinine.

The CTCAE will be applied for laboratory tests related to renal effects (Table FRCF.5.4). This CTCAE grading scheme is consistent with both Version 3.0 and Version 4.03 of the CTCAE guidelines.

Shift tables will show the number and percentage of subjects from baseline to maximum during Period 2 and 3, with baseline depicted by highest grade during the baseline period. A shift table summary displaying the number and percentage of subjects with maximum postbaseline results will be presented by treatment group within the following categories:

- Decreased; postbaseline category < baseline category
- Increased; postbaseline category > baseline category
- Same; postbaseline category = baseline category.

Treatment-emergent lab abnormalities related to elevated creatinine occurring at any time during the Dosing Period will be tabulated using the CTCAE grades shown in Table FRCF.5.4. Planned and unplanned measurements will be included.

Treatment-emergence will be characterized using 5 criteria:

- any increase in postbaseline CTCAE grade from worst baseline grade
- increase to Grade 1 or above at worst postbaseline
- increase to Grade 2 or above at worst postbaseline
- increase to Grade 3 or above at worst postbaseline
- increase to Grade 4 at worst postbaseline.

Table FRCF.5.4	Common Terminology Criteria for Adverse Events (CTCAE) Related
	to Renal Effects

Lab Test	CTCAE Version	Grade	Criteria in SI or CN Units
Elevated creatinine	3.0	0 (normal)	\leq ULN
		1	$>$ ULN and $\leq 1.5 \times$ ULN
		2	$>1.5 \times$ ULN and $\leq 3 \times$ ULN
		3	$>3\times$ ULN and $\leq 6\times$ ULN
		4	>6× ULN

Abbreviations: CN = conventional (US); CTCAE = Common Terminology Criteria for Adverse Events; SI = Système International; ULN = upper limit of normal.

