5.7.3. Clinical Laboratory Evaluation

Laboratory analyses will include planned analytes only. Planned analytes are those specified in the protocol. Summaries will be provided in both Système International (SI) and United States (US) conventional (CN) units (when different). Limits from the performing lab will be used to define low and high. Analyses of laboratory values will be produced using the measurements collected at scheduled time points. All unscheduled assessments will appear only in data listings.

- **Box plots for observed values:** Values at each visit (starting at randomization) will be displayed in box plots for patients who have both a baseline and a result for the specified visit. Unplanned measurements will be excluded. Original-scale data will be used for the display. These box plots will be used to evaluate trends over time and to assess a potential impact of outliers on central tendency summaries. The box plot will be a notched box for each treatment with outliers displayed, individual measurements outside of reference limits will also be displayed using distinct symbols overlaying the box plot, and descriptive summary statistics will be included in a table below the box plot.
- **Box plots for change values:** Change from baseline to each visit will be displayed in box plots for patients who have both a baseline and a result for the specified visit. Change from baseline to last observation will also be summarized and analyzed for patients who have both baseline and at least 1 postbaseline result. Baseline will be the last non-missing observation in the baseline period. The last non-missing observation in the Dosing Period will be used as the last observation. Unplanned measurements will be excluded. The box plot will be a notched box for each treatment with outliers displayed, change from baseline to last observation will be summarized within the box plot of changes (rightmost column), and descriptive summary statistics will be included in a table below the box plot, along with a p-value using the ANCOVA model containing terms for treatment and the continuous covariate of baseline measurement. Type III sums of squares will be used. The significance of within-treatment group LSMean changes from baseline are different from zero using a t-statistic. In addition to the LSMeans and tests, the SD, minimum, Q1, median, Q3, and maximum will be displayed.

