Alanine aminotransferase (ALT), aspartate aminotransferase (AST), and total bilirubin will not be included in this analysis as different ranges will be used as described in Section 5.7.5.

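### SAP 5.7.6.2 does not say whether creatinine maxima are taken within each crossover period; read literally with the Week 0 grouping rule, the by-treatment tables lose most of any drug effect

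*SAP*

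**What the plan says.** **Creatinine (SAP 5.7.6.2).** The shift is defined this way: "Shift tables will show the number and percentage of subjects from baseline to maximum during Period 2 and 3". Its starting point is a single grade per subject, "with baseline depicted by highest grade during the baseline period". The summary of maximum postbaseline results "will be presented by treatment group within the following categories". Treatment-emergent abnormalities are those "occurring at any time during the Dosing Period", and unplanned measurements count. The SAP does not define Dosing Period. SAP 5.7.2 uses the words baseline period for the time up to the first dose of study medication.

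**Last observation (SAP 5.7.3).** "The last non-missing observation in the Dosing Period will be used as the last observation". Change to that value is analysed by ANCOVA on treatment and baseline. SAP 5.7.4 applies the same methods to vital signs.

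**Grouping.** SAP 5.7 analyses safety data by the product to which the patient was randomized at Week 0. SAP 5.3.1 and Protocol 9.3 analyse the Safety population by the intervention actually received within each study period. These two rules differ once participants cross over.

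**Period rules elsewhere.** SAP 5.7.2 counts TEAEs by period. SAP 5.3.2 gives Period 3 its own baseline, the last value before its first dose.

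**Liver (SAP 5.7.6.1).** The section names "change from the baseline value to the maximum value during Period 2 and 3", and the matching minimum, and sends the method to 5.7.3. Threshold elevations "will be listed for both Period 2 and 3", patient by patient.

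**The concern.** Under SAP 4.1, each participant who completes both periods receives 12 weeks of LY3454738 and 12 weeks of placebo. A single maximum over both periods therefore belongs to neither treatment. If the columns are the Week 0 arms, they are the two sequences, and completers in both have had the same two courses in opposite order. A drug effect on creatinine would raise both columns and largely drop out of the comparison.

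What is at stake is the creatinine grade-shift and treatment-emergent tables. They matter because 5.7.6.2 counts unplanned measurements, whereas 5.7.3 sends unscheduled laboratory values to listings only. A spike caught between visits would be tabulated here and not in the by-visit plots.

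**Working it through.** **Inputs from the documents.** Allocation is 3:1 of about 60 randomized, so about 45 and 15 (SAP 4.1, 4.2). About 52 are expected to be evaluable (Protocol 9.2), so the non-evaluable share is 8/60 = 13.3%. The half-life is about 2 weeks (Protocol 4.2). The last Period 2 infusion is at Week 10 and the first Period 3 infusion at Week 12, with no washout (Protocol 1.3). The plan gives no creatinine event rate or power figure, so there is nothing of its own to reproduce on this point.

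**Assumed inputs.** Per-period risks p0 (placebo) and p1 (drug); the share d leaving before Period 3, taken as 0, 13.3% and 25%; and a carryover fraction f, the part of the excess risk that drug-first participants keep in Period 3, taken as 0, 25% and 50%. The plan does not say when non-evaluable participants leave, so using 13.3% for d is an assumption.

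**Reading 1: one maximum over both periods, columns by Week 0 arm.**

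- Completer, either order: 1 − (1 − p0)(1 − p1).
- Leaver: p1 if drug-first, p0 if placebo-first.
- Difference between columns without carryover: d × (p1 − p0).
- Carryover adds (1 − d)(1 − p1) × f × (p1 − p0).

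At p1 = 15%, p0 = 5%, d = 0, f = 0: 1 − 0.85 × 0.95 = 0.1925, or 19.3% in both columns. Expected counts are 45 × 0.1925 = 8.7 and 15 × 0.1925 = 2.9. Period 2 alone would expect 45 × 0.15 = 6.75 and 15 × 0.05 = 0.75.

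Differences in percentage points:

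| p0, p1 | Period 2 only | Combined, d = 0 | d = 13.3% | d = 25% | d = 0, f = 25% to 50% |
|---|---|---|---|---|---|
| 2%, 10% | 8 | 0 | 1.1 | 2.0 | 1.8 to 3.6 |
| 5%, 15% | 10 | 0 | 1.3 | 2.5 | 2.1 to 4.3 |
| 5%, 30% | 25 | 0 | 3.3 | 6.3 | 4.4 to 8.8 |

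Independence between periods sets the 19.3% level. Equality of the columns at d = 0 does not need it; it needs only that order makes no difference.

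**Reading 2: one maximum over both periods, columns by treatment received.** The maximum spans both treatments, so it cannot be assigned to a column.

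**Reading 3: a maximum within each period, but the baseline of 5.7.6.2.** In Period 2 the comparison is sound. In Period 3, a grade rise on drug that persists past Week 12 is counted again as a rise on placebo. At a 2-week half-life, the share of the level after the Week 10 dose still present is 50% at Week 12, 25% at Week 14, 12.5% at Week 16 and 3% at Week 20. In the 15% versus 5% example, the drug-first group's placebo period reads 0.05 + f × 0.10, which is 7.5% at f = 25% and 10% at f = 50%, instead of 5%.

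**Last observation in 5.7.3.** If the Dosing Period ends at Week 24, a completer's last value is on the crossed-over treatment, while the ANCOVA column is the Week 0 arm. For a mean effect δ that does not persist after switching, completers contribute −δ and leavers +δ. The expected difference is −(1 − 2d)δ, which is −δ at d = 0 and −0.73δ at d = 13.3%: the sign is reversed.

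**Liver.** SAP 5.7.6.1 refers to 5.7.3 for change to minimum and maximum and for treatment-emergent high or low results. SAP 5.7.3 describes only values and changes by visit and change to last observation. It also says that ALT, AST and total bilirubin "will not be included in this analysis as different ranges will be used as described in Section 5.7.5", and SAP 5.7.5 is Immunogenicity. No analysis of liver maxima by treatment is specified anywhere.

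**The case against.** The strongest reply is that the SAP nowhere says the periods are combined. SAP 5.7.1 summarises exposure in both periods by treatment group, which is naturally a per-period display. SAP 5.3.1, 5.3.2 and 5.7.2 and Protocol 9.3 are all period-specific, and 5.7 points to 5.3.2 for the baseline. Under that reading nothing cancels in Period 2. This stands as far as it goes: the combined maximum is an inference from 5.7.6.2 together with the Week 0 rule in 5.7. It does not clear the text, because 5.7.6.2 states its own baseline rule (highest grade in the baseline period), which differs from the Period 3 baseline in 5.3.2, and because 5.7 and 5.3.1 conflict on grouping.

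A reader might go further and infer that a drug effect cancels out entirely, for both creatinine and liver tests, so that the laboratory safety output would reassure whatever the drug does. The documents do not support that:

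- Cancellation is exact only without early exits, carryover or period effects. With no washout, some carryover is plausible.
- Both columns would rise, which is visible even though it could not be attributed to the drug.
- Creatinine by visit, with its ANCOVA, still shows Period 2 mean changes, and TEAEs are counted by period.
- The liver threshold results are patient listings, which cannot cancel between columns.

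It is also fair that no test is attached to the creatinine tables, that creatinine is not among the adverse events of special interest in Protocol 8.3.7, and that every risk used above is assumed.

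**Conclusion.** The point holds for creatinine as a conditional one. Followed literally with the Week 0 grouping in 5.7, the shift and treatment-emergent tables retain only about the fraction d of a true Period 2 difference: none if nobody leaves early, 13% at d = 13.3%, 25% at d = 25%, and somewhat more with carryover. With treatment-received grouping, the combined maximum has no column to go in. With per-period maxima, the stated baseline double-counts persisting rises in Period 3. Each reading needs a correction, so this is more than a missing detail.

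The undefined Dosing Period carries the problem into the last-observation analyses of 5.7.3 and, through 5.7.4, vital signs. The loss is confined to the maximum, shift, treatment-emergent and last-observation displays. For liver tests the defect is a different one: an analysis that is named but not written, behind a broken cross-reference.

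The sizes rest on assumed risks, dropout and carryover. The direction rests only on the crossover and on reading 5.7.6.2 together with 5.7.

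**What to change.** In the SAP:

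1. Derive maximum, last observation, CTCAE shift and treatment-emergence separately within Period 2 and Period 3, by treatment received in that period. Use the pre-dose baseline for Period 2 and the 5.3.2 baseline for Period 3. Replace Dosing Period and the combined-period wording accordingly.
2. Make Period 2 the randomized drug–placebo comparison. Show Period 3 descriptively by sequence, because its Week 12 baseline is an on-drug value for the drug-first group.
3. Reconcile the Week 0 grouping in 5.7 with 5.3.1 and Protocol 9.3.
4. State how the 30-day post-dose follow-up in 5.7 attaches to each period. Counted from the last Period 2 infusion at Day 71 it would run to Day 101, past the first Period 3 infusion at Day 85.
5. Write out the liver change-to-minimum and change-to-maximum analysis by period, for all four analytes, and correct the cross-references between 5.7.3, 5.7.5 and 5.7.6.1.

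The cost is SAP wording and more table shells, with no new data collection. The downside is small Period 3 groups: at most about 15 participants would be on drug in that period.

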5.7.6.3. Infections

Infections will be defined using the PTs from the MedDRA Infections and Infestations SOC, with additional terms from the Investigations SOC being used in selected instances, as described below.

Treatment-emergent infections will be analyzed according to various groups of infectious events including:

- all infections
 - o all PTs in the Infections and Infestations SOC,
- serious infections
 - o all PTs in the Infections and Infestations SOC that are SAEs,
- infections that require therapeutic intervention (antibiotics, antivirals, antifungals, and so on)
 - all PTs in the Infections and Infestations SOC for which there is an antimicrobial concomitant medication associated with that event for that subject,
- herpes zoster
 - specific Lilly-defined PTs from the Herpes Viral Infections high-level term (HLT) in the Infections and Infestations SOC, shown in Appendix 1,
- tuberculosis
 - specific Lilly-defined PTs from the Tuberculous Infections HLT and the Investigations SOC, shown in Appendix 2
- viral hepatitis
 - all PTs from the Hepatitis Viral Infections HLT (HLT code 10057212) in the Infections and Infestations SOC.

J1B-MC-FRCF (c) Statistical Analysis Plan Version 2

For each infection event, the frequency for each PT will be provided, ordered by decreasing frequency in the LY3454738 highest dose group by infection group: all infections, serious infections (overall and on each approach to identifying SAEs), infections that require therapeutic intervention, herpes zoster infections, tuberculosis, and viral hepatitis.

In addition to the incidence of infectious AEs by MedDRA PT as described above, the number and percentage of subjects with treatment-emergent infectious AEs by treatment group will be summarized and listed.

Potential Opportunistic Infections:

Potential opportunistic infections (POIs) will be identified according to 2 different approaches.

POIs are identified from TEAEs based on a Lilly-defined list of MedDRA PTs, shown in the Appendix 3. These PTs are a subset of terms from the Infections and Infestations SOC.

For the POIs identified from MedDRA PTs, the number and percentage of subjects overall and for each specific PT will be summarized by treatment group, with specific event terms ordered by decreasing frequency in the LY3454738 highest dose.

Association of Infections with Lymphopenia or Neutropenia:

The relationship between the occurrence of lymphopenia and neutropenia with the occurrence of infections will be evaluated based on case reviews. Inferential analyses and/or graphical displays may be conducted if warranted. Infection outcomes considered for this analysis are any infection, any serious infection, infections that require therapeutic intervention (antibiotics, antivirals, antifungals, and so on), tuberculosis, herpes zoster, and viral hepatitis.

5.7.6.4. Allergic Reactions/Hypersensitivities

A search will be performed using the current MedDRA version 20.0 SMQs to search for relevant events, using the following queries:

- Anaphylactic reaction SMQ (2000021)
- Hypersensitivity SMQ (20000214)
- Angioedema SMQ (2000024)

Events that satisfy the queries will be listed, by temporal order within patient ID, and will include SOC, PT, SMQ event categorization including detail on the scope (narrow or broad), reported AE term, AE onset and end dates, severity, seriousness, outcome, etc.

5.8. Protocol Deviations

Protocol deviations will be tracked by the clinical team, and their importance will be assessed by key team members during protocol deviation review meetings. Out of all important protocol deviations (IPDs) identified, a subset occurring during Period 2 prior to the primary endpoint (Week 12) with the potential to affect efficacy analyses will result in exclusion from the PP population.

Potential examples of deviations include patients who receive excluded concomitant therapy, significant non-compliance with study medication (<80% of assigned doses taken, failure to take study medication and taking incorrect study medication), patients incorrectly enrolled in the study, and patients whose data are questionable due to significant site quality or compliance issues. Refer to a separate document for the important protocol deviations.

The number and percentage of patients having IPD(s) will be summarized within category and subcategory of deviation by treatment group for Period 2 using the mITT population. Individual patient listings of IPDs will be provided. A summary of reasons patients were excluded from the PPS will be provided by treatment group.

5.9. Interim Analyses and Data Monitoring

The assessment committee is authorized to evaluate unblinded interim efficacy and safety analyses. Study sites will receive information about interim results ONLY if they need to know for the safety of their patients.

Unblinding details are given in a separated unblinding plan.

Analysis for the primary database lock will be conducted when all participants have completed the Period 2 (or discontinued Period 2 treatment). An interim analysis prior to the primary database lock may be conducted when approximately 50% of the participants have had the opportunity to complete Period 2 (including those who discontinued Period 2 treatment). Other interim analyses may be conducted as needed. All interim analyses will be used to support planning activities associated with the development program. No adjustment of type I error will be performed.

The assessment will be conducted by an internal assessment committee with a limited number of prespecified team members who do not have direct site contact or data entry/validation responsibilities. A limited number of pre-identified individuals may gain access to the limited unblinded data, as specified in the unblinding plan, prior to the interim or final database lock.

Ongoing monitoring of safety data (including AEs, SAEs, and selected laboratory measurements) will continue throughout the study using blinded data. Interim safety analyses may be conducted to review unblinded safety data. The analyses will be conducted and reviewed by an internal assessment committee composed of personnel who do not have direct site contact or data entry/validation responsibilities.

Details of the planned interim data analyses and the assessment committee data review process are included in an assessment committee charter.

5.10. Annual Report Analyses

Annual report analyses, such as the Development Update Safety Report (DSUR), will be documented in a separate document.

5.11. Clinical Trial Registry Analyses

Additional analyses will be performed for the purpose of fulfilling the Clinical Trial Registry (CTR) requirements.

Analyses provided for the CTR requirements include a summary of AEs, provided as a dataset which will be converted to an XML file. Both SAEs and 'Other' AE are summarized: by treatment group, by MedDRA PT.

- An AE is considered 'Serious' whether or not it is a TEAE.
- An AE is considered in the 'Other' category if it is both a TEAE and is not serious. For each SAE and 'Other' AE, for each term and treatment group, the following are provided:
 - the number of participants at risk of an event
 - the number of participants who experienced each event term
 - the number of events experienced.
- Consistent with www.ClinicalTrials.gov requirements, 'Other' AEs that occur in fewer than 5% of patients/patients in every treatment group may not be included if a 5% threshold is chosen (5% is the minimum threshold).
- AE reporting is consistent with other document disclosures for example, the CSR, manuscripts, and so forth.

Similar methods will be used to satisfy the European Clinical Trials Database (EudraCT) requirements.

6. References

- [2007 Expert Panel] 2007 Expert Panel Report 3: Guidelines for the Diagnosis and Management of Asthma Summary Report 2007. Available at: https://www.nhlbi.nih.gov/health-topics/guidelines-for-diagnosis-management-of-asthma or *J Allergy Clin Immunol*. 2007;120(5 suppl):S94-S138.
- ClinicalTrials.gov. NCT03580369. Available at: https://clinicaltrials.gov/ct2/show/NCT03580369?term=ligelizumab&rank=5. Accessed July, 2019.
- ClinicalTrials.gov. NCT03580356. Available at: https://clinicaltrials.gov/ct2/show/NCT03580356?term=ligelizumab&rank=6. Accessed June, 2019.
